1.1.5. Use of chemoradiotherapy in adjuvant and neo-adjuvant therapy

Several studies have evaluated the use of neoadjuvant protocols combining pre-operative radiotherapy with chemotherapy. One study assessed a regimen of three cycles of pre-operative doxorubicin, ifosfamide and dacarbazine (“MAID”) chemotherapy, with radiation therapy. Subjects with positive surgical margins received additional post-operative radiation, and subjects received an additional three cycles of post-operative MAID therapy³⁰. Subjects enrolled had intermediate or high-grade (grade II or III) tumors at least 8 cm in maximal dimension. The treatment group of 48 subjects was compared to 48 historical controls, 12 of whom had received some form of adjuvant chemotherapy. Controls were subjects from the same institution who were matched with respect to tumor size, grade, age at diagnosis, and era of treatment.

While the primary endpoint was not explicitly stated, positive margins were observed in 15% (7/48) of the experimental treated subjects at the time of surgery versus 19% (9/48) of the matched controls. There was no difference in the rate of local control between the two groups. Distant metastasis-free, disease-free and overall survival however heavily favored the group treated with the MAID regimen. The non-randomized nature of the study implies that the results must be taken with caution.

This regimen was assessed again in a retrospective review of subjects treated more recently at the same institution³¹. No control group was presented in this analysis. Surgical margins were positive in 11% of resection specimens. Local and distant metastasis-free rate at 5 years was 91 and 64%. The authors attempted to identify factors associated with clinical outcomes using Cox

analysis but were unable to identify any factors in the dataset analyzed. Again, it is difficult to evaluate the value of this chemoradiotherapy treatment regimen due to lack of an adequate control group.

A prospective study from a single center evaluated pre-operative administration of doxorubicin, followed by a 10-day regimen of radiotherapy, in subjects to undergo sarcoma resection³². 75 subjects were enrolled in the study. Tumors were greater than 5 cm in 66% of the subjects and intermediate- or high-grade (grade II/III) in 71%. In 11% (8/75), surgical margins were positive for residual sarcoma. Subjects with positive margins had 5-year local control of only 50%, versus 97% for those with negative margins. Tumor grade and tumor stage (reflecting tumor size, depth and anatomic extent of involvement) were associated with the risk of death in multivariable Cox analysis. Wound complications occurred in 11 (15%) of the 75 subjects, including 3 subjects requiring re-operation. Like the studies above, interpretation of this one is hampered by lack of a control group.

A retrospective analysis examined results of 112 subjects treated with various neoadjuvant chemoradiotherapy regimens, neoadjuvant radiation, or with surgery alone³³. All three treatment groups had high rates of margin negativity at the time of surgery (86-91%). For all subjects, there was no difference in rate of local control rate, distant metastasis free survival or overall survival. For those with primary tumors greater than 5 cm, overall survival was superior when the radiation-treated groups were compared to those treated only with surgery. However, only 7 subjects treated with surgery alone fell into this group.

A great deal of work has been undertaken, primarily using the anthracycline doxorubicin alone and in combinations (especially with ifosfamide), to evaluate the value of peri-operative cytotoxic therapy in soft tissue sarcomas. Use of this drug in peri-operative setting is problematic. While this drug is among the most active as monotherapy for sarcomas, it can cause a dose-dependent cardiomyopathy⁵. This limits the lifetime dose of the drug, as excessive amounts can cause treatment-refractory heart failure. Doxorubicin can also be associated with enhancement of radiation-associated skin toxicity³⁴. In the absence of proven peri-operative benefit, use of doxorubicin alternatives would be sensible: this would reserve the agent for treatment of metastatic disease in those later developing metastatic disease and avoid the risk of cardiotoxicity in the subjects who did not have recurrent disease. Further, the results cited earlier indicating that tumoral biology is a key determinant of outcome suggest that agents exploiting sarcoma and radiation biology might be very desirable to explore in combination regimens of radiotherapy and systemic therapy.

Even if a subject is ultimately cured of the condition, treatment can have lifelong impact. Surgery remains the mainstay of treatment. Due to the relatively advanced condition that subjects often present with, surgery to render subjects disease-free is often cosmetically and functionally disfiguring. While rehabilitation is a key component of the treatment process, it cannot entirely solve the deficits consequent to proper sarcoma treatment.

Radiation therapy (RT) is a critical component of optimal sarcoma therapy. While occasionally used as definitive therapy, RT is more often used in coordination with surgery. Administered neoadjuvantly or adjuvantly, RT improves local control, and may allow tumors initially considered unresectable to be removed successfully. Although based on retrospective analysis,

recent data from one group suggest that peri-operative RT may also convey a survival benefit. This remains to be confirmed by additional analyses.

Surgery combined with radiation therapy provides excellent local disease control, providing definitive local control in about 85-90% of subjects. Results with high-risk tumors are less successful. "High-risk" tumors are those that are large (generally greater than 5 cm in maximal dimension), high histologic grade, and/or located in surgically challenging positions. Further, these therapies do not address the major reason for the ultimate failure of treatment in most cases: distant metastasis. Approaches to improve local control and simultaneously address distant treatment failure are needed. Systemic therapy approaches may be most useful for this.

Up to now, peri-operative systemic therapy of sarcomas has demonstrated clear benefit only in sarcomas associated with childhood: osteosarcoma, Ewing's sarcoma, and rhabdomyosarcoma. In these diseases, this therapy has both a local control and distant control advantage, leading to marked improvements in survival over local therapy alone. Similar benefits have not been demonstrated through use of current agents in the majority of STS.

Systemic, peri-operative therapy of most STS is reserved for those with high-risk tumors likely to pose difficulties in complete surgical extirpation. Combination therapy, typically with Adriamycin and ifosfamide (a regimen known as "AIM"), yields a significant response rate (estimated ORR about 26%). A treatment response may improve the quality of subsequent local therapy with surgery and radiation therapy. Whether such therapy impacts control of distant micro-metastatic disease is unclear.

AIM poses several problems in this setting:

- i) While it has the highest documented response rate of any general STS regimen, it is still only 26%. Benefit can only be determined empirically. Thus, subjects must suffer the significant toxicity and logistical complexity of the regimen in exchange for, more likely than not, no discernible benefit.
- ii) Adriamycin, an important component of the regimen, is incompatible with concurrent RT. Thus, any possible synergism to be derived from concurrent chemoradiotherapy is lost.
- iii) Traditionally, peri-operative systemic therapy regimens have been derived from those with previously demonstrated activity in the metastatic setting. In the metastatic setting, a clear survival benefit for AIM therapy over Adriamycin monotherapy has been excluded. Clear evidence of survival benefits for Adriamycin-based, peri-operative systemic therapy is lacking, despite significant efforts. If such benefit exists, it is modest, at best.
- iv) If effects on distant disease are a major focus of peri-operative systemic therapy, then Adriamycin monotherapy might be considered. However, response rates for Adriamycin monotherapy are only about 10%. Administration of Adriamycin monotherapy as an alternative to AIM in the

peri-operative setting would sacrifice one of the few documented benefits of multi-agent therapy with AIM: its increased response rate.

- v) AIM is relatively toxic therapy. Subjects must be in good physical condition with good performance status and end-organ function to be considered for this therapy. Due to either disease status or co-morbidities, subjects may not be able to receive AIM therapy.

New approaches to peri-operative systemic therapy of STS are desperately needed.

1.2. Cabozantinib Background

Cabozantinib (XL184) is an inhibitor of multiple receptor tyrosine kinases (RTKs). It is provided as both capsules and tablets, but the two formulations are not interchangeable. Cometriq® (cabozantinib capsules, 140 mg) was approved by the United States Food and Drug Administration (FDA) on 29 November 2012 for the treatment of subjects with progressive, metastatic medullary thyroid cancer (MTC). On 21 March 2014, cabozantinib capsules were approved by the European Commission for the treatment of adult subjects with progressive, unresectable locally advanced or metastatic MTC. Cabometyx™ (cabozantinib tablets, 60 mg) was approved by FDA on 25 April 2016 for subjects with advanced renal cell carcinoma (RCC) who have received prior anti-angiogenic therapy and by the European Commission on 09 September 2016 for the treatment of advanced RCC in adults who have received prior vascular endothelial growth factor (VEGF)-targeted therapy.

The targets of cabozantinib include several RTKs known to play important roles in tumor cell proliferation and/or tumor neovascularization, namely MET (hepatocyte growth factor [HGF] receptor), vascular endothelial growth factor receptor 2 (VEGFR2, also known as KDR), AXL, and RET. Other recognized targets of cabozantinib include ROS1, TRKA, TRKB, TYRO3, MER, two additional members of the VEGFR family (VEGFR1, VEGFR3), and the closely-related RTKs KIT and FLT-3. In vivo pharmacodynamic activity of cabozantinib against MET, VEGFR2, AXL, and RET has been demonstrated in preclinical studies and has been associated with tumor growth inhibition and tumor regression. In preclinical studies, cabozantinib treatment has also been shown to inhibit tumor angiogenesis and tumor invasiveness and metastasis.

In nonclinical toxicology studies of cabozantinib in rodents and non-rodents, histopathological changes associated with cabozantinib administration were observed in gastrointestinal (GI) tract, bone marrow, lymphoid tissues, kidney, adrenal, and reproductive tract tissues, and secondary changes were observed in bone and pancreas. Cabozantinib tested negative in bacterial and mammalian cell genotoxicity assays *in vitro*. In reproductive toxicity studies, cabozantinib was embryotoxic in rats, produced fetal soft tissue changes in rabbits, produced fetal external malformations in rats, and decreased fertility in male and female rats. The metabolite present at highest concentrations in humans administered cabozantinib, EXEL-1644, was negative in an *in vitro* bacterial genotoxicity bioassay and caused no systemic tissue toxicity in rats. In a 2-year rat carcinogenicity study, cabozantinib-related neoplastic findings consisted of an increased incidence of benign pheochromocytoma, alone or in combination with malignant pheochromocytoma/complex malignant pheochromocytoma of the adrenal medulla in both sexes. No clinical cases of pheochromocytoma have occurred to date. No carcinogenic

signal was observed in a rasH2 transgenic mouse model following cabozantinib dosing for 26 weeks.

1.3. Rationale for Combination of Cabozantinib with Radiation Therapy for High-Risk Soft Tissue Sarcoma of the Extremities

Given the established benefit of combination surgery and radiation therapy, systemic agents that increase the therapeutic index of radiotherapy in this relatively radio-resistant class of tumors would be desirable. This would be most important in cases where surgical excision is likely to be complex. In addition, agents that might treat pre-existing micro-metastatic disease would also be desirable.

Targeting the MET oncogene represents a strategy to achieve some of these goals in the sarcoma setting. MET dysregulation appears to be important and frequent in the STS pathogenesis, including in clear cell sarcoma³⁵, synovial sarcoma³⁶, leiomyosarcoma³⁷, pleomorphic sarcoma^{37,38,39}, rhabdomyosarcoma^{40,41}, angiosarcoma³⁸, epithelioid³⁶, Ewing's⁴², and alveolar soft part sarcoma⁴³. A phase II study was conducted with the MET inhibitor tivantinib, enrolling 47 subjects, primary with alveolar soft part sarcoma and clear cell sarcoma⁴⁴. These diseases were targeted due to their association with microphthalmia transcription factor (MiTF). MiTF proteins lead to transcriptional activation of the MET gene. Among those with alveolar soft part sarcoma (n=27), median progression-free survival was 5.5 months. At least three studies are in progress to assess the activity of the MET inhibitor cabozantinib in advanced sarcomas (See ClinicalTrials.gov: NCT01755195, NCT01979393, NCT02867592). None of these seek to assess administration of the agent in combination therapy regimens or with neoadjuvant intent.

MET inhibitors also have documented radiosensitizing effects. Pre-clinical studies demonstrating such effects have been undertaken in non-small cell lung cancer^{45,46} and prostate cancer⁴⁷. Several mechanisms have been invoked for these radiosensitizing effects. These include: prevention of radiation-induced MET expression via the ATM-NFKB pathway, thereby preventing MET-mediated cell invasion; and anti-apoptotic effects⁴⁸ and down-regulation of the ATR-CHK1-CDC25 pathway⁴⁹. Critically, the latter mechanism enhances radiosensitivity in p53-deficient cells, a common circumstance in sarcomas.

This trial will examine cabozantinib in combination with radiotherapy in the neoadjuvant setting. Because of concerns regarding potential toxicities of the combination of a multi-targeted tyrosine kinase inhibitor like cabozantinib with radiotherapy (such as fistula formation⁵⁰), this study will be restricted to those with sarcomas of the extremities. Fistula formation has also been reported in studies of cabozantinib monotherapy⁵¹. The subject population to be enrolled will include all sarcoma subjects for whom neoadjuvant radiation to the extremities followed by surgical resection is planned.

The results of this study may help to determine whether concurrent administration of cabozantinib and radiotherapy is feasible, and whether there is preliminary evidence of activity in this class of tumors. Correlative studies will utilize specimens that are available pre-treatment, at the time of resection, and at recurrence, if recurrence occurs. These studies will investigate changes in molecular pathway activation during therapy; correlates of response or

lack thereof; and alterations in the immune microenvironment induced by this therapy. In addition, these studies will investigate radiomic metrics correlating with treatment response and relapse-free survival.

1.4. Rationale for Starting Dose Selection

Cabozantinib is presently approved for the treatment of advanced renal cell carcinoma that has progressed despite prior anti-angiogenic therapy and hepatocellular carcinoma (HCC) that has been previously treated with sorafenib⁵¹. Recommended dose is 60 mg daily. The drug is available in 20 mg tablets. Dose reductions to 40 mg and 20 mg daily are possible in response to toxicity in the currently approved setting. Below 20 mg daily, the drug is discontinued in the currently approved setting.

In this study, we propose to initiate treatment using a 21-day dosing schedule. The following dose levels will be assessed:

Dose Level	Daily Dose of Cabozantinib
-1	20 mg Daily
0	40 mg Daily
+1	60 mg Daily

Dose level +1 is the presently approved target dose of cabozantinib⁵¹. Based on the reported half-life of the drug (99 hours⁵¹), dose reductions below 40 mg daily would be reasonable to consider, if the initial 40 mg daily dosing is not tolerated. These would result in lower steady state concentrations of the drug. Since one of the primary endpoints is to assess the radiosensitizing effects of cabozantinib, it would still be reasonable to explore doses that are less than would be administered when the drug is being used as monotherapy, if the full dose is not tolerable.

2. STUDY OBJECTIVES AND ENDPOINTS

2.1. Objectives

2.1.1. Primary Objectives

- Phase I: To determine if administration of cabozantinib is safe and feasible in combination with neoadjuvant radiation therapy.
- Phase II: To assess the proportion of subjects alive and free of both local and distant disease recurrence (and progression after incomplete resection) one year after treatment initiation.

2.1.2. Secondary Objective(s)

- Rate of pathologic response.
- Rate of surgical excision with negative margins.
- Response rate (complete, partial, overall) of the combination therapy prior to surgery, as defined by RECIST 1.1 criteria.
- Pattern of and time to local vs. distant recurrences.
- Relapse-free and overall survival at various time points from study entry.
- Safety and tolerability of combined treatment regimen, including the rate of discontinuation during the cabozantinib monotherapy component of the study.

2.1.3. Exploratory Objective(s)

- Comparison of pre- and post-treatment specimens to identify changes in activation of molecular pathways associated with MET genetic profiles associated with treatment response and with relapse-free survival.
- Evaluation of pre- and post-treatment specimens for mutational status of signaling pathways, including MAP-Kinas and AKT/m-TOR pathways.
- Explore changes in the immune microenvironment induced by this neoadjuvant treatment, in comparison to matched specimens obtained from the University of Washington pathology archives.
- Radiomic studies to identify predictors of treatment response and relapse-free survival.

2.2. Endpoints

2.2.1. Primary Endpoints

- Phase I: Recommended Phase 2 dose of cabozantinib in combination with radiation
- Phase II: Rate of relapse at 12 months after treatment initiation.

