TITLE	A Phase I/II Study of Neoadjuvant Cabozantinib in Combination with Radiation Therapy for Sarcomas of the Extremities
PROTOCOL NUMBER	RG1003562 (CC10051)
PHASE OF DEVELOPMENT	1/2
STUDY OBJECTIVES	
Primary Objective(s)
 
Phase I: To determine if administration of cabozantinib is safe and feasible in combination with neoadjuvant radiation therapy.Phase II: To assess the proportion of subjects alive and free of both local and distant disease recurrence (and progression after incomplete resection) one year after treatment initiation. 
Secondary Objective(s)
 
Rate of pathologic response.Rate of surgical excision with negative margins.Response rate (complete, partial, overall) of the combination therapy prior to surgery, as defined by RECIST 1.1 criteria.Pattern of and time to local vs. distant recurrences.Relapse-free and overall survival at various time points from study entry.Safety and tolerability of combined treatment regimen, including the rate of discontinuation during the cabozantinib monotherapy component of the study. 
Exploratory Objective(s)
 
Comparison of pre- and post-treatment specimens to identify changes in activation of molecular pathways associated with MET genetic profiles associated with treatment response and with relapse-free survival.

	
• Evaluation of pre- and post-treatment specimens for mutational status of signaling pathways, including MAP-Kinase and AKT/m-TOR pathways.• Explore changes in the immune microenvironment induced by this neoadjuvant treatment, in comparison to matched specimens obtained from the University of Washington pathology archives.• Radiomic studies to identify predictors of treatment response and relapse-free survival.

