Follow-up Period	Follow-up period is the on-study time period after the EOT Visit. All subjects that discontinue study drug and have not withdrawn full consent to participate in the study will continue in the follow-up phase for disease recurrence. Follow up will continue approximately every 12 weeks (± 2 weeks), until either one (1) year has elapsed since initiation of cabozantinib therapy (C1D1), death, withdrawal of consent, disease recurrence, or the study closes, whichever is the earliest. This will include a physical exam and imaging assessment. Thereafter, subjects who will be followed every 6 months (+/- 1 month) until 3 years have elapsed since initiation of cabozantinib therapy (C1D1), end-of-study, death, or withdrawal of consent, whichever is earliest. This evaluation may be made by review of publicly available information, record review and/or telephone contact.
Primary Analysis	For this study will occur once all data for primary and secondary endpoints is collected.
Efficacy Analysis Dataset	This includes all subjects treated with at least one dose of cabozantinib at the recommended phase 2 dose, concurrently with neoadjuvant radiation therapy.
Full Analysis Set	All enrolled subjects who receive at least 1 dose of cabozantinib (treated population). Subjects enrolled to Phase 1 who withdraw for reasons other than toxicity during the DLT Period will be considered not evaluable and will be replaced.

Per-protocol Analysis Set	All enrolled subjects who do not have any prospectively defined protocol violations. Subjects enrolled to Phase 1 or Phase 2 who are unable to tolerate cabozantinib monotherapy will not be considered evaluable for the Phase 1 or 2 component of the study and will be replaced. Subjects enrolled to Phase 1 who withdraw for reasons other than toxicity during the DLT Period will be considered not evaluable and will be replaced.
Progression-free survival	The time from the first dose date to the first observation of a disease progression or death due to any cause.
Overall survival	The time from the first dose date to the date of death due to any cause.

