12.2. Efficacy Analysis

Assessment of the primary efficacy analysis will take place in real time. Based on anticipated accrual of 40 evaluable subjects, if 9 or more have relapsed or died due to any cause (unless clearly documented as unrelated to investigational diagnosis, e.g., car accident) at or before one year after cabozantinib initiation, then the study will be closed to further accrual, and data will simply be collected on the remaining subjects, as specified in the protocol.

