12.4. Sample Size Considerations

Phase 1: up to 12 subjects to identify the MTD, but the MTD may be reached with as few as 5 subjects.

Phase 2: For sample size determination, we assume the following:

- Null hypothesis: 1-yr relapse-free survival (local and distant) =75%
- Alternative hypothesis: 1-yr relapse-free survival (local and distant) =90%
- Alpha=0.1 (one-sided).
- Beta=0.1 (power=90%)

Total accrual=40 evaluable subjects.

Anticipate accrual of 6 evaluable subjects from phase I component of study. Therefore, 34 evaluable subjects to accrue in phase II portion of study. Subjects who withdraw for reasons other than toxicity during the DLT Period will be determined to be not evaluable and will be replaced.

Subjects are evaluated for efficacy assessment if they receive at least one dose of cabozantinib in combination with neoadjuvant radiation therapy.

Assuming a 10% drop-out/non-evaluable rate, 44 total subjects would be accrued to the efficacy component for the study to yield 40 evaluable subjects.

From the perspective of efficacy, this study is intended as a screening study of activity. Thus, avoiding a type II error (rejecting the proposed regimen as inactive, when it is an active regimen) is a major consideration. This study is not intended to provide definitive evidence of activity. Therefore, a type I error (false positive) is not considered as critical. For these reasons, we have chosen to increase the power of the study to 90% (minimizing type II errors), while relaxing constraints regarding type I. Specifically, we use a one-sided alpha of 0.10 for rejection of the null hypothesis. Use of a one-sided value is justified based on the high efficacy for *local* control of soft tissue sarcoma provided by the combination of surgery and neoadjuvant radiation therapy (~90%). It is not anticipated that distant disease control would be worsened by addition of cabozantinib to neoadjuvant radiation therapy.

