An early stopping rule for accrual to the efficacy component of the study is to be undertaken. If 9 (nine) or more evaluable subjects are found to have died or demonstrated disease recurrence at or before 1 (one) year after cabozantinib initiation, then the efficacy component of the study will be discontinued. This assumes of a binomial probability for the primary endpoint, with a target probability of 0.90 for evaluable subjects to be alive and disease-free at one-year after initiation of cabozantinib therapy. When 9 subjects demonstrate failure with respect to the primary endpoint (disease recurrence or death from any cause), then the upper bound of the 95% confidence interval for the binomial probability distribution would no longer encompass the target probability of 0.90 ($31/40=0.775$, 95%CI:0.62-0.89). At this point, the study would be considered negative with respect to the primary endpoint, and further accrual will be discontinued.

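### The Phase II primary-endpoint event is defined inconsistently: sections 12.2 and 12.4 state the same 9-failure accrual stop but treat an unrelated death differently, and 2.2.1 does not mention death.

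*Combined protocol and SAP*

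**What the plan says.** The event that counts as a Phase II failure is worded in four ways.

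- **Objective** (synopsis and 2.1.1): the "proportion of subjects alive and free of both local and distant disease recurrence (and progression after incomplete resection) one year after treatment initiation". Any death is a failure, because the subject must be alive.
- **Endpoint** (synopsis and 2.2.1): "Phase II: Rate of relapse at 12 months after treatment initiation". Death is not mentioned.
- **12.2 Efficacy Analysis**: accrual closes once 9 or more of the anticipated 40 have "relapsed or died due to any cause (unless clearly documented as unrelated to investigational diagnosis, e.g., car accident") by one year. An unrelated death is exempt.
- **12.4 Sample Size Considerations**: the same 9-failure stop, explained as "failure with respect to the primary endpoint (disease recurrence or death from any cause"). There is no exception.

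The hypotheses in 12.4 are set on relapse-free survival; the null is "1-yr relapse-free survival (local and distant) =75" percent. The glossary defines progression-free survival ("The time from the first dose date to the first observation of a disease progression or death due to any cause") and overall survival. It expands the abbreviation RFS but does not define it.

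**The concern.** Two analysts who each follow a section of the plan can count failures differently from the same data, and nothing ranks one section above another. The difference rests on a cause-of-death judgement in an open-label, single-arm study. At stake directly is whether accrual closes. At one remove is the test of 75%, for which the plan prints no pass mark, so a reader must also supply the rule to which the count is applied.

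**Working it through.** **Inputs from 12.4:** null rate 0.75, alternative 0.90, one-sided alpha 0.10, power 0.90, N=40 evaluable, stop at 9 failures, and 31/40=0.775 with 95% CI 0.62–0.89. **Assumed, because the documents give no figure:** unrelated deaths of 0.5, 1 or 2.5 percentage points within the total failure rate.

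**1. Definitions side by side**

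| Place | Recurrence | Unrelated death | Progression after incomplete resection |
|---|---|---|---|
| Synopsis objective, 2.1.1 | failure | failure | failure |
| Synopsis endpoint, 2.2.1 | failure | not mentioned | not mentioned |
| 12.2 | failure | exempt | not mentioned |
| 12.4 | failure | failure | not mentioned |

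**2. Reproduce the plan.** Let F be the number of failures in 40, binomial. The pass mark is the largest c with P(F≤c | 0.25) ≤ 0.10.

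- P(F≤6 | 0.25) = 0.0962 and P(F≤7 | 0.25) = 0.1820, so c=6.
- Power is P(F≤6 | 0.10) = 0.9005.
- The exact (Clopper-Pearson) 95% interval for 31/40 is 0.6155–0.8916, matching the printed 0.62–0.89.

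The plan's N and interval therefore reproduce, and its inputs imply success at no more than 6 failures in 40.

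**3. The accrual stop.** Take 8 recurrences and 1 unrelated death.

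- 12.4 counts 9 failures: 31/40, upper limit 0.892, which excludes 0.90. Accrual closes.
- 12.2 counts 8 failures: 32/40, upper limit 0.909, which includes 0.90. Accrual continues.

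The stop is a count of failures, so this holds whether or not the exempted subject stays in the denominator. Both counts already exceed 6, so only the stop changes.

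**4. The test of 75%.** Take 6 recurrences and 1 unrelated death.

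- Death counted (12.4, 2.1.1): 33/40, p=0.182, not rejected.
- Death exempted and the subject kept as a success: 34/40, p=0.096, rejected.
- Death exempted and the subject dropped: 33/39, p=0.111, not rejected. There is no reversal.

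**5. How often the test would differ, if exempted subjects stay as successes.** Let π be the total failure rate and u the unrelated-death part. The count without unrelated deaths is binomial with rate π−u and never exceeds the full count. So P(results differ) = P(F≤6 | π−u) − P(F≤6 | π).

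| u | π=0.25 | π=0.10 |
|---|---|---|
| 0.005 | 0.1088 − 0.0962 = 0.013 | 0.019 |
| 0.01 | 0.1227 − 0.0962 = 0.027 | 0.036 |
| 0.025 | 0.1727 − 0.0962 = 0.076 | 0.072 |

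The value 0.025 means 40 × 0.025 = 1 expected unrelated death among 40 subjects in a year.

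**The case against.** The strongest defence is that the exception in 12.2 is an accrual rule and no more. That section opens with the primary efficacy analysis, but its only stated consequence is closing accrual. The one sentence that expressly defines failure on the primary endpoint is in 12.4. It agrees with the objective, and 12.4 ties the 0.90 target to being alive and disease-free. The study is also described as a screen for activity in which a false positive is not considered critical, and unrelated deaths within a year should be few in a population of performance status 0 or 1.

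Most of this stands, and it limits the point. It does not remove the conflict over the stop, because 12.4 states that same rule without the exception.

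Four stronger readings are tempting and are not supported:

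- *One unrelated death necessarily reverses the test of 75%.* This requires both carrying the 12.2 exemption (or the literal 2.2.1 wording) into the test and keeping the subject as a success. The documents state neither.
- *The sections contradict each other on progression after incomplete resection.* The objective names it and the later sections are silent; none excludes it.
- *A subject who progresses before surgery would lack a scheduled scan at 12 months.* Footnote h of Table 2 ends imaging at recurrence or progression. But the glossary, 6.2.5, 6.4.2 and footnote k continue 12-weekly imaging to one year or recurrence, without naming progression as an end.
- *The 90% was set on a narrower event, so N must grow.* Nothing suggests this, and 12.4 points the other way.

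**Conclusion.** The inconsistency is real and should be fixed. The direct conflict is the accrual stop: at 8 recurrences plus 1 unrelated death, 12.4 closes accrual and 12.2 leaves it open. Away from that boundary, one such death does not change the stop.

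The effect on the test of 75% is conditional. With exempted subjects kept as successes, and unrelated deaths assumed at 0.5 to 2.5 points, the definitions give different results in about 1% to 8% of trials at the null failure rate of 25% and 2% to 7% at the alternative of 10%. The pass mark of 6 is derived from the plan's inputs and is not printed in it.

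The plan also does not say how to score progression before surgery or a subject never resected, although "Subjects are evaluated for efficacy assessment if they receive at least one dose of cabozantinib in combination with neoadjuvant radiation therapy". That is a gap to settle in the same definition, not part of the contradiction.

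**What to change.** - Define 12-month relapse-free survival once, from C1D1: free of local or distant recurrence, of progression after incomplete resection (as in 2.1.1), and of death from any cause.
- Use that definition in the synopsis, glossary, 2.2.1, 12.2 and 12.4, and delete the unrelated-death exception in 12.2.
- In the same definition, state how progression before surgery and non-resection by 12 months are scored.
- Print the success criterion implied by the plan's own inputs: at most 6 failures in 40, exact one-sided alpha 0.096, power 0.9005.

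The cost is wording only, with no new assessments. The downside is that the observed rate may be slightly less favourable than under the exemption.
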